7.1 DISCONTINUATION OF STUDY INTERVENTION/EXPERIMENTAL MANIPULATION

Stop rules. If the PI, IRB and/or SMC determines that stop rules are warranted for serious adverse events then data collection and study enrollment will be stopped. The SMC and the IRB will be asked to review the study and suggest modifications of the protocol, the threshold limit or other changes. If the SMC and the Chairperson of the IRB believe that these modifications are adequate for resumption of the study, then the study will resume. NINR will receive a written report within three days of any such suspension and/or resumption of data collection.

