4 STUDY DESIGN

4.1 OVERALL DESIGN

STUDY DESCRIPTION.

Our overall goal is to develop and test **BREATHE-PEDS (BRief intervention to Evaluate Asthma THErapy-Pediatrics)**, a shared decision-making intervention, among low-income urban minority adolescents with uncontrolled asthma.

AIMS. 1) develop **BREATHE-PEDS** in a pediatric population (dyads of caregivers and their 10- to 14-year-old early adolescents with uncontrolled asthma) receiving asthma care in FQHCs; 2) evaluate the feasibility and acceptability of intervention procedures; and 3) assess intervention effects on asthma outcomes (monthly x 3 months post-intervention).

HYPOTHESES.

1. The intervention will be feasible and acceptable as evidenced by: high rates of dyad recruitment and retention; PCP fidelity to the intervention protocol; and PCP and caregiver-child dyad satisfaction.
2. Over 3-months post-intervention, relative to controls, **BREATHE-PEDS** children will have improvement (a) in asthma control as measured by the *Asthma Control Questionnaire*⁶³⁻⁶⁵ (primary outcome), higher perceived SDM, and (b) on other asthma outcomes (secondary outcomes), including quality of life, school absences, lung functioning, and exacerbation.

STUDY PHASE. Phase 1 development and testing a behavioral intervention

STUDY DESIGN. This is a group-randomized clinical trial.

STUDY PROCEDURES.

Aim 1: Focus Groups.

Focus groups. Prior to recruiting for the trial, we will hold focus groups with caregivers (n =20); early adolescents (n =20) and dyads (n =10) (N=60), separately .

Aims 2 & 3: Group-randomized trial. This is a trial of a behavioral/educational intervention comparing the active condition **BREATHE-PEDS (BRief intervention to Evaluate Asthma THerapy-Peds)** to a dose-matched attention control condition (see below for detailed description of conditions). Active and control interventions are delivered once in 9-minutes by the participants' PCP during a single office visit. In each condition there are matched data collection points after baseline: 1-month 2-month, 3-month post-intervention. Considering the potential for visit disruptions due to Covid-19, we offer an alternative plan for the delivery of the intervention at a single telehealth visit (baseline) by phone or HIPAA-compliant videoconferencing platform.

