8.1.4 ADVERSE EVENT REPORTING

AEs and SAEs will be systematically assessed at all data collection points via review of the medical record and/or patient interview. Subjects will be instructed to report AEs and SAEs to the study team within 48 hours of their occurrence.

During the trial, subjects will be instructed to notify the study team within 48 hours of any Emergency Department (ED) visit or hospitalization, regardless of its cause, and to notify the study team within 48 hours of initiating oral corticosteroids (OCS), each event representing the standard definition of asthma exacerbation. Because not all exacerbations cause individuals to seek acute care, we will track OCS use and intensification of beta-agonist use as those who manage an exacerbation outside of the ED or hospital will manage their exacerbation in this manner. We will also ask subjects to report these at monthly data collection points in an attempt to capture any exacerbations that might otherwise go unreported. In this manner we will not miss any exacerbations. Subjects' answers will then be compared to the medical record and/or claims data, as available.

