8.1.5 SERIOUS ADVERSE EVENT REPORTING

SAE reporting.

Any SAE whether related to study intervention, will be reported to the IRB and the SMC. The PI will inform the IRB and SMC immediately and jointly decide whether the reported event is a SAE that must be reported to NINR due to the unexpectedness and/or the severity of the event. If it is determined that it is either unexpected and/or the severity, the SAE will be reported to NINR within two days.

In the event that a patient either withdraws from the study or the investigator decides to discontinue a patient due to SAE, the patient will be monitored by the investigator via ongoing status assessment until 1) a resolution is reached, i.e., the problem requiring hospitalization has resolved or stabilized with no further changes expected; 2) the SAE is determined to be clearly unrelated to the study intervention; or 3) the SAE results in death. A summary of the SAEs that occurred during the previous year will be included in the annual progress report to the IRB and the SMC. The report will include the participants' sociodemographic characteristics, expected versus actual recruitment rates, treatment retention rates, any quality assurance or regulatory issues that occurred during the past year, summary of AEs and SAEs, and any actions or changes with respect to the protocol.

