While we anticipate the intervention will improve asthma control and reduce asthma morbidity, it is possible that study participants have more AEs than controls because of an increased awareness of the role of their suboptimal self-management in uncontrolled asthma. Therefore, the DSMB/SMC will also monitor for reverse effects.

During the trial, participants will be instructed to notify the study team within 48 hours of any ED visit or hospitalization, regardless of its cause, and to notify the study team within 48 hours of initiating OCS or excessive intensification of rescue medication (to be defined by the DSMB/SMC), each event representing the standard definition of asthma exacerbation. We will also ask participants to report these events within 48 hours of their occurrence, but we will also query about these events at each data collection point to capture any exacerbations that might otherwise go unreported. Participants' answers will then be compared to the medical record and/or claims data, as available. Exacerbation rates more than the threshold set by the DSMB/SMC may trigger an immediate study shutdown.

The DSMB/SMC will determine how an AE is to be categorized using standard taxonomy: Unrelated (clearly not related to the research), Unlikely (doubtfully related to the research), Possible (may be related to the research), Probable (likely related to the research) and Definite (clearly related to the research). They will also address Unanticipated Problems (UP). In this study we will also use the FDA definition of a SAE: deaths, hospitalization, toxicity, all life threatening or disabling/incapacitating events, and all congenital abnormalities or birth defects among research participants.

UPs, AEs, & SAEs

The DSMB/SMC will adhere to the Office of Human Research Protections (OHRP) definitions for AEs, SAEs, and UPs using the following OHRP definitions:

AEs are defined as UPs involving risks to study participants or others, or as any untoward medical occurrence that may present itself during the study period which may or may not have a causal relationship with the treatment. Such events may also include breaches of confidentiality.

SAEs result in any of the following outcomes: death, a life-threatening experience, inpatient hospitalization, or a significant disability/incapacity.

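### As written, the section 7.1 stop rule pauses scheduled safety assessment in children who have already had the one-time intervention

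*Combined protocol and SAP*

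**What the plan says.** Section 7.1 states the consequence of a safety stop: if the PI, the IRB or the SMC determines that "stop rules are warranted for serious adverse events then data collection and study enrollment will be stopped". The SMC and IRB are then asked to review the study and suggest changes, and the study resumes if they find those changes adequate. The section closes with "NINR will receive a written report within three days of any such suspension and/or resumption of data collection", so pausing data collection is intended and not a slip of wording. No exception is made for dyads already in follow-up, and no limit is put on the length of the pause.

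Section 8.1.4 describes how harms are found: "AEs and SAEs will be systematically assessed at all data collection points via review of the medical record and/or patient interview". On exacerbations it adds: "We will also ask subjects to report these at monthly data collection points in an attempt to capture any exacerbations that might otherwise go unreported". It also has a participant-initiated route: "Subjects will be instructed to report AEs and SAEs to the study team within 48 hours of their occurrence".

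The data and safety monitoring text in section 10.1 repeats the 48-hour instruction and the query at each data collection point. It also says: "Exacerbation rates more than the threshold set by the DSMB/SMC may trigger an immediate study shutdown". It does not say what happens then to children already seen.

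Section 4.1 fixes the exposure: "Active and control interventions are delivered once in 9-minutes by the participants' PCP during a single office visit". Assessments follow at 1, 2 and 3 months.

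**The concern.** A stop for harm normally aims to prevent further exposure while keeping watch on those already exposed. Here the exposure is a single 9-minute conversation. Once it has taken place, stopping data collection does not reduce what the child has received; it only ends scheduled observation.

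The timing is the difficulty. Children enter with uncontrolled asthma (section 2.3.1), and section 10.1 accepts that the intervention could have reverse effects, which the DSMB/SMC is to monitor. Under 7.1, once a signal has led to a stop, the contacts that actively look for further events are suspended. The SMC and IRB must then judge modification or resumption without new scheduled data from the children best placed to confirm or refute the signal. Monthly ACQ scores falling due in the pause may not be recoverable.

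**Working it through.** The protocol gives no figure on this point, so there is none to reproduce. The main check is textual.

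1. **What stops.** Section 7.1 names data collection and enrolment. Its heading concerns discontinuation of the intervention, but its text does not say whether delivery of the intervention stops.
2. **What depends on data collection.** Systematic AE/SAE assessment by record review and/or interview, and the monthly exacerbation query, both take place at the data collection points (8.1.4; section 10.1).
3. **Consequence of 1 and 2.** Following 7.1 literally suspends scheduled safety ascertainment for every dyad in follow-up.
4. **What remains.**
   - The 48-hour instruction is neither cancelled nor expressly continued during a suspension.
   - For a participant who withdraws or is discontinued because of an SAE, "the patient will be monitored by the investigator via ongoing status assessment until 1) a resolution is reached" (8.1.5, repeated in section 10.1), or until the SAE is judged clearly unrelated or results in death. This does not reach the other children in follow-up.
   - The synopsis allows exacerbations to be taken from provider notes in the electronic record, with confirmation from claims where available. That may recover events later.
5. **What is not replaced.** None of these is a scheduled contact with each exposed child during the pause, and none supplies an ACQ score.

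For scale only, with inputs:
- N = 85 dyads (synopsis; section 5.1 and the power calculation use 80).
- Follow-up of 3 months, with assessments at 1, 2 and 3 months (sections 4.1 and 8).
- Accrual period A = 6 months. This is an assumption: the synopsis gives about 6 months as clinician participation, not as an accrual period.
- Even accrual, counted from the intervention visit, with no attrition.

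Dyads in follow-up at a halt in month t = (N/A) × min(t, 3).
- A = 6, t from 3 to 6: 85/6 × 3 = 42.5.
- A = 6, t = 1.5: 85/6 × 1.5 = 21.25, which is everyone seen so far.
- N = 80, A = 6, t from 3 to 6: 80/6 × 3 = 40.
- Other accrual periods, N = 85, once 3 months have passed: A = 4 gives 63.75, A = 9 gives 28.3, A = 12 gives 21.25.

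Assessments falling due after a halt in months 3 to 6 (A = 6). The 42.5 dyads divide evenly into those with 3, 2 and 1 assessments left, about 14.2 each.
- First month of pause: one assessment per dyad, 42.5.
- Second month: 2/3 × 42.5 = 28.3.
- Third month: 1/3 × 42.5 = 14.2.
- Total if the halt is never lifted: 42.5 × (3 + 2 + 1)/3 = 85.

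For a halt at month 4, 85 × 4/6 = 56.7 dyads have been seen, with 56.7 × 3 = 170 follow-up assessments scheduled. A two-week pause touches about 21 (21.25/170 = 12.5%), a one-month pause about 42 (25%), and a permanent halt 85 (50%). With A = 12, the permanent-halt total is 21.25 × 2 = 42.5.

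**The case against.** A reader might infer that children already seen lose all safety follow-up. The documents do not support that. The 48-hour instruction is separate from the scheduled visits and 7.1 does not cancel it; section 10.1 makes the MPIs responsible for safety daily; and record and claims extraction may recover acute-care events afterwards. The children also remain under their usual PCP, since section 6.1.1 says neither intervention alters clinical care. These points stand and narrow the loss to active, scheduled ascertainment. They do not remove it: the protocol adds the monthly query because self-report can miss events, and later extraction does not inform a review held during the pause.

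A reader might also take 85 assessments, or half of those scheduled, as the expected loss. Section 7.1 describes a suspension that can be lifted, and 7.3 calls for missed visits to be rescheduled, so 85 is a ceiling. Still, 7.1 sets no time limit, and section 10.1 has the board meeting twice a year, more if needed.

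A third inference is that cutting ACQ follow-up biases the arm comparison. That is not shown. A study-wide halt falls on both arms on one calendar date and is triggered by study-level events. It resembles administrative censoring, and the mixed models in section 9.4.1 are intended to accommodate data missing at random.

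Finally, operative rules are left partly to the SMC: section 2.3.1 asks it whether stop rules are needed, and section 10.1 has it define them and finalise a charter and monitoring plan not reproduced here. Those could provide for continued follow-up. The shutdown sentence in section 10.1 is also discretionary and does not itself say that follow-up ends. Both points are fair, but neither changes the default written in 7.1.

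**Conclusion.** The point holds in limited form. As written, a stop under 7.1 suspends scheduled AE/SAE assessment and the monthly exacerbation query in children who have already had their only intervention visit, without reducing their exposure, while the SMC and IRB are deciding what to do next. Other reporting routes limit the loss but do not fill the gap.

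Under even accrual of 85 dyads over about 6 months, a halt in months 3 to 6 affects about 42 dyads: about 42 assessments in the first month of pause and at most about 85. The number of dyads in follow-up ranges from about 64 (4-month accrual) to about 21 (12-month accrual). The textual conclusion does not depend on these figures. For the ACQ comparison, the supportable consequence is lost precision.

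**What to change.** Amend 7.1 so that a stop does not end data collection for dyads already seen. The planned 1-, 2- and 3-month assessments, the 48-hour event notification and record review would continue unless the SMC or IRB directs otherwise. Bring the shutdown sentence in section 10.1 and the ascertainment text in 8.1.4 into line, and adjust the closing sentence of 7.1 on reporting to NINR, which now refers to suspension of data collection.

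Separately, reconcile the heading of 7.1, which concerns discontinuing the intervention, with its text, which names only data collection and enrolment, so that it is clear whether delivery of the intervention stops. No rule is proposed on that.

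The cost is a sentence or two in 7.1 and matching wording in the monitoring plan. The downside is that surveys already planned continue during a pause.

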7.2 PARTICIPANT DISCONTINUATION/WITHDRAWAL FROM THE STUDY

Participants are free to withdraw from participation in the study at any time upon request.

7.3 LOST TO FOLLOW-UP

A participant will be considered lost to follow-up if he or she fails to return for TBD number of scheduled visits and study staff are unable to contact the participant after more than 3 attempts.

The following actions must be taken if a participant fails to return for a required study visit:

- The site will attempt to contact the participant, reschedule the missed visit, counsel the participant on the importance of maintaining the assigned visit schedule and ascertain if the participant wishes to and/or should continue in the study

- Before a participant is deemed lost to follow-up, the investigator or designee will make every effort to regain contact with the participant (where possible, 3 telephone calls and, if necessary, a certified letter to the participant's last known mailing address or local equivalent methods). These contact attempts will be documented in the participant's medical record or study file.
- Should the participant continue to be unreachable, he or she will be considered to have withdrawn from the study with a primary reason of lost to follow-up.

8 STUDY ASSESSMENTS AND PROCEDURES

Caregivers and children will complete assessments at four timepoints: baseline, immediately after the medical visit, and 1-, 2-, and 3-months following the child's asthma visit. The baseline and 1

The measures completed at each time point by each participant are detailed in the table below as well as in the endpoints section on pages 3-5.

MEASURE	TIMEPOINT						COMPLETED BY		
	Screening	Base	Immed	1-Mon	2-Mon	3-Mon	Caregiver	Child	Clinician
Asthma Control Questionnaire	X	X		X	X	X	X	X	
Shared-Decision-Making Questionnaire			X				X	X	X
Medication Adherence Record Scale-Asthma		X		X	X	X	X	X	
Conventional & Alternative Management for Asthma	X	X		X	X	X	X	X	
Pediatric Asthma Quality of Life Questionnaire		X		X		X		X	
Pediatric Asthma Caregiver's Quality of Life Questionnaire		X		X		X	X		
Asthma Impairment & Risk Questionnaire (AIRQ)		X		X	X	X		X (>12-years-old)	
Brief debriefing survey			X				X	X	X

Asthma exacerbation				X	X	X	X		
Asthma Responsibility Questionnaire		X		X	X	X		X	
Newest Vital Sign		X					X		
Short Assessment of Health Literacy							X		
Asthma Prevention Index		X		X	X	X	X	X	
Asthma history & demographics		X					X	X	

8.1 ADVERSE EVENTS AND SERIOUS ADVERSE EVENTS

8.1.1 DEFINITION OF ADVERSE EVENTS

Adverse events are defined as unanticipated problems involving risks to study participants or others, or as any untoward medical occurrence that may present itself during the study time period which may or may not have a causal relationship with the treatment.

8.1.2 DEFINITION OF SERIOUS ADVERSE EVENTS

Serious adverse events result in any of the following outcomes: death, a life-threatening experience, inpatient hospitalization, or a significant disability/incapacity. Such events also include breeches of confidentiality.

8.1.3 CLASSIFICATION OF AN ADVERSE EVENT

8.1.3.1 SEVERITY OF EVENT

All AEs should be assessed by the principal investigator, and if necessary, another professional with clinical Moderate adverse events are those discomforts severe enough to cause interference with usual activities or requiring treatment by a health care provider. Such events also include the loss of participants from the study for reasons related in any way to a deviation from procedures for ensuring confidentiality.

Mild adverse events are those events that are easily tolerated signs or symptoms of discomfort; minor irritants that cause no loss of time from normal activities; symptoms that require no medication or a medical evaluation; and transient signs and symptoms.

8.1.3.2 RELATIONSHIP TO STUDY INTERVENTION/EXPERIMENTAL MANIPULATION

The SMC will then determine how an AE is to be categorized using standard taxonomy: Unrelated (clearly not related to the research), Unlikely (doubtfully related to the research), Possible (may be related to the research), Probable (likely related to the research) and Definite (clearly related to the research).

8.1.3.3 EXPECTEDNESS

Unexpected adverse events are those events, the specificity or severity of which is not consistent with the risk information described in the general investigative plan or the IRB proposal. "Unexpected" refers to an adverse event that has not been previously observed.

Expected adverse events are those events, the specificity or severity of which is consistent with the risk information described in the general investigative plan or IRB proposal.

Any ED visit or hospitalization associated with primary ICD-10-CM Diagnosis Code 493. Asthma (493.00 asthma atopic unspecified; 493.01 asthma atopic asthmaticus; 493.02 asthma atopic acute exacerbation; 493.10 intrinsic asthma unspecified; 493.11 intrinsic asthma asthmaticus; 493.12 intrinsic asthma acute exacerbation; 493.20 asthma chronic obstructive pulmonary disease copd; 493.21 asthma chronic obstructive pulmonary disease copd; 493.22 asthma chronic obstructive pulmonary disease copd; 493.81 exercise induced bronchospasm; 493.82 cough variant asthma; 493.91 asthma bronchial allergic nos asthmaticus; 493.92 asthma bronchial allergic nos acute exacerbation) will be characterized as a Probable or Definite SAE.

8.1.4 ADVERSE EVENT REPORTING

AEs and SAEs will be systematically assessed at all data collection points via review of the medical record and/or patient interview. Subjects will be instructed to report AEs and SAEs to the study team within 48 hours of their occurrence.

During the trial, subjects will be instructed to notify the study team within 48 hours of any Emergency Department (ED) visit or hospitalization, regardless of its cause, and to notify the study team within 48 hours of initiating oral corticosteroids (OCS), each event representing the standard definition of asthma exacerbation. Because not all exacerbations cause individuals to seek acute care, we will track OCS use and intensification of beta-agonist use as those who manage an exacerbation outside of the ED or hospital will manage their exacerbation in this manner. We will also ask subjects to report these at monthly data collection points in an attempt to capture any exacerbations that might otherwise go unreported. In this manner we will not miss any exacerbations. Subjects' answers will then be compared to the medical record and/or claims data, as available.

8.1.5 SERIOUS ADVERSE EVENT REPORTING

SAE reporting.

Any SAE whether related to study intervention, will be reported to the IRB and the SMC. The PI will inform the IRB and SMC immediately and jointly decide whether the reported event is a SAE that must be reported to NINR due to the unexpectedness and/or the severity of the event. If it is determined that it is either unexpected and/or the severity, the SAE will be reported to NINR within two days.

In the event that a patient either withdraws from the study or the investigator decides to discontinue a patient due to SAE, the patient will be monitored by the investigator via ongoing status assessment until 1) a resolution is reached, i.e., the problem requiring hospitalization has resolved or stabilized with no further changes expected; 2) the SAE is determined to be clearly unrelated to the study intervention; or 3) the SAE results in death. A summary of the SAEs that occurred during the previous year will be included in the annual progress report to the IRB and the SMC. The report will include the participants' sociodemographic characteristics, expected versus actual recruitment rates, treatment retention rates, any quality assurance or regulatory issues that occurred during the past year, summary of AEs and SAEs, and any actions or changes with respect to the protocol.

